#### **9.6.3.3 Serious Adverse Events**

All AEs will be assessed as either serious or non-serious. An SAE is defined as any untoward medical occurrence that at any dose:

- Results in death
- Is immediately life threatening, (the term "life threatening" in the definition of "serious" refers to an event in which the subject is at risk of death at the time of the event; it does not refer to an event which hypothetically might have caused death if it were more severe)
- Requires in patient hospitalization or prolongation of existing hospitalization (hospitalization for elective surgery for a baseline condition is not considered an AE)
- Results in persistent or significant disability/incapacity (permanent or substantial disruption of a person's ability to conduct normal life functions)
- Is a congenital anomaly/birth defect
- Is a medically important event that may not be immediately life threatening or result in death or hospitalization but may jeopardize the subject and may require medical or surgical intervention to prevent one of the above listed outcomes. Examples of such events include, but are not limited to, allergic bronchospasm requiring intensive treatment in an emergency room or at home; blood dyscrasias or convulsions that do not result in inpatient hospitalization.

Note: A spontaneous abortion will be considered an SAE, and must be reported per Reporting of SAEs under Section 9.5.3.6.

#### **9.6.3.4 Assessment of Severity**

The severity assigned to an AE should be determined by the maximum severity of the AE. The categories described below should be used to estimate the severity of AEs:

- **Mild:** Transient or mild discomfort; no limitation in activity; no medical intervention/therapy required
- **Moderate:** Mild to moderate limitation in activity; some assistance may be needed; no or minimal medical intervention/therapy required
- **Severe:** Marked limitation in activity; some assistance usually required; medical intervention/therapy required; hospitalization or prolongation of current hospitalization possible; may be incapacitating or life threatening

### **9.6.3.5 Assessment of Causality**

The PI should assess the relationship of the AE to the study drug as either “Related” or “Not Related”. The following should be taken into account when assessing AE causality:

- **Related:** There is at least a reasonable possibility that the AE/SAE is related to the study drug. Reasonable possibility means that there is evidence to suggest a causal relationship between the drug and the AE.
- **Not Related:** There is little or no reasonable possibility that the AE/SAE is related to the study drug. This assessment implies that the AE/SAE has little or no temporal relationship to the study drug and/or a more likely or certain alternative etiology exists.

### **9.6.3.6 Reporting of Serious Adverse Events**

Adverse events classified as “serious” require expeditious handling and reporting to Sponsor or designee within 24 hours of investigational center notification to comply with regulatory requirements.

All SAEs, whether related or unrelated to study drug, must be immediately reported to the ethica CRO within 24 hours of the PI’s awareness of the event. All SAEs must be reported via confirmed facsimile or email transmission and must be submitted on a written SAE report form signed by the PI within 24 hours of the PI’s awareness of the event. **Please refer to the SLI-C40-001 Safety and Medical Monitoring Plan for the listing of appropriate contacts.**

PIs should not wait to receive additional information to fully document the event before notifying ethica CRO of an SAE. If only limited information is initially available, follow-up reports are required. Additional relevant information such as hospital records and autopsy reports should be provided to the Sponsor as soon as they are available. Should the PI become aware of an SAE (regardless of its relationship to IP) that occurs within 30 days after stopping the study drug, the SAE must be reported in accordance with procedures specified in this protocol.

All deaths of subjects, regardless of cause, and which are known to the PI will be reported on the appropriate CRF for up to 30 days after the administration of study drug, regardless of the PI's opinion regarding drug relationship. Documentation of the subject's cause of death and a copy of the autopsy/hospital report will also be provided. The Medical Monitor must be notified within 24 hours of knowledge of the event by telephone (and/or fax/email) of all subject deaths. Written follow-up must be received by ethica CRO within five (5) calendar days of initial notification.

The PI should take all appropriate measures to ensure the safety of the subjects, notably he/she should follow a subject with an SAE until the event has resolved or the condition has stabilized. This may imply that follow-up will continue after the subject has left the study, and that additional investigations may be requested by the Sponsor. When an SAE persists at the end of the study, the PI will conduct follow-up contacts with the subject until the PI/Sponsor agree the event is satisfactorily resolved and/or stabilized. If at any time after 30 days after administration of study drug, the PI becomes aware of an SAE which he/she feels is related to study drug or procedure, this must also be reported immediately (within 24 hours of knowledge of occurrence) by telephone and confirmed facsimile transmission/email to ethica CRO.

### **9.6.3.7 Expedited Serious Adverse Event Reports**

Expedited SAE reports are those that are both unexpected based on the reference document (Investigator Brochure) and are related (i.e., the relationship cannot be ruled out) to the study drug.

These expedited reports are subject to reporting timelines of 7 and/or 15 calendar days to the regulatory reporting agency(ies). The Sponsor will notify regulatory authorities of these SAEs and all participating investigational centers in writing for submission by the PI to the IRB.

Upon receiving such notices, the PI must review and retain the notice with the Investigator Brochure and immediately submit a copy of this information to the responsible IRB according to local regulations. The PI and IRB will determine if the informed consent requires revision. The PI should also comply with the IRB procedures for reporting any other safety information.

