### **9.6.3 Adverse Events**

During Parts A and B, all observed or volunteered AEs regardless of treatment group or suspected causal relationship to the study treatment will be recorded in the eCRF. Subjects will be questioned for the occurrence of any new or worsening signs or symptoms at each visit.

During Part B Extension, all Treatment-Related AEs (TRAEs) will be recorded in the eCRF. Subjects will be questioned for the occurrence of any new or worsening signs or symptoms at each visit.

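### Relatedness is defined at two different thresholds, the causality scale has no place for the procedure, and the Extension keeps no adverse event record of incision events attributed to surgery

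*Protocol*

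**What the plan says.** **Causality scale (Protocol 9.6.3.5).** "The PI should assess the relationship of the AE to the study drug as either" related or not related; there is no third level and no other object of attribution. Related requires at least a reasonable possibility, which is then explained: "Reasonable possibility means that there is evidence to suggest a causal relationship between the drug and the AE". The opposite category reads "There is little or no reasonable possibility that the AE/SAE is related to the study drug". It is said to imply a weak or absent temporal link, or that "a more likely or certain alternative etiology exists", or both.

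**Expedited reports (9.6.3.7).** These are SAEs that are unexpected against the Investigator Brochure and that "are related (i.e., the relationship cannot be ruled out) to the study drug".

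**SAE notification (9.6.3.6).** Every SAE goes to the CRO within 24 hours, related or not. For events more than 30 days after study drug there is a further trigger: "an SAE which he/she feels is related to study drug or procedure". Section 3.3 has the Medical Monitor evaluate SAEs on receipt against the expedited reporting requirements.

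**Part B Extension (9.6.3).** "During Part B Extension, all Treatment-Related AEs (TRAEs) will be recorded in the eCRF". The abbreviations list spells out TRAE but gives no threshold and does not say whether treatment means the drug, the procedure or both. Section 6.8 limits Extension medication records in the same way, to medication for a TRAE.

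**The concern.** One word carries two meanings in adjacent sections. The PI's code and the regulatory test can therefore disagree on the same SAE, and no section says which wording prevails or who resolves the difference. This is a first-in-human study (Section 1) without a data monitoring committee (Section 12.5), so consistent expediting matters.

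The second difficulty is attribution. Every treated site is a surgical wound, so surgery is a ready alternative cause for local events, and the Part A excisions are done for the study. Yet the scale records the drug only.

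The third concerns the Extension. The design separates drug from surgery by comparing the two halves of one incision. Section 10.3 has Part B local events recorded per side for that purpose. In the Extension, the PI's causality judgement is applied first, and an event judged surgical is dropped before the halves can be compared. The PI does not know which half received SLI-F06, so that judgement cannot draw on the treatment allocation.

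**Working it through.** No arithmetic underlies the definitions, so the check sets the sections side by side for each type of event.

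| Event | 9.6.3.5 (PI's scale) | 9.6.3.7 (expedited, if serious and unexpected) | Agree? |
|---|---|---|---|
| (a) Evidence suggests the drug | Related | Related | Yes |
| (b) Little possibility, no positive evidence, drug not excludable | Not Related | Related | **No** |
| (c) Drug excluded | Not Related | Not related | Yes |

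Row (b) is the grey zone. It includes an SAE for which surgery is the more likely cause but the drug cannot be excluded.

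A fourth case, (d), is a late SAE that the PI attributes to the procedure and not to the drug. It is reportable under 9.6.3.6, but 9.6.3.5 offers no way to record that attribution. Its TRAE status in the Extension is undefined.

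**Where case (b) has an effect.** The 24-hour rule in 9.6.3.6 covers SAEs whatever their causality, so a case (b) SAE still reaches the CRO and the Medical Monitor. What remains open is whether it is expedited. Section 3.3 assigns the review but gives no causality standard, and no section describes a separate sponsor assessment of causality.

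**What the Extension records for an incision event attributed to surgery:**

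- Kept by side: POSAS and photographs. The subject grades left and right separately, PI and subject both grade paired 5 cm sections (9.5.2.1, 9.5.2.2), and the half-to-half PI score is the primary efficacy outcome (4.2.2).
- Not kept: an AE record with diagnosis, onset, seriousness and corrective treatment, the items that 9.6.3.2 collects for an AE. Medication for the event is not kept either (6.8).
- Already elicited: under 9.6.3, subjects are asked about new or worse symptoms at every Extension visit.

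**Ceiling on exposure.** About 25 subjects × 4 scheduled visits (Months 15, 18, 21, 24) = about 100 subject-visits, plus any optional visit. The true number is likely to be lower: entry is by consent, the first Extension visit may be later than Month 15, and visits may be cancelled (9.4). Up to 6 subjects may have a history of hypertrophic or keloidal scarring (4.2.1). The documents give no event rate, so the number of grey-zone SAEs or unrecorded local events cannot be derived.

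**The case against.** The strongest reply is that the two sections serve different steps. Section 9.6.3.5 instructs the PI, 9.6.3.7 describes what the Sponsor sends to regulators, and a lower bar at the later step is cautious. All SAEs arrive whatever their code, and 9.6.3.6 refers to a Safety and Medical Monitoring Plan, not at hand, that may set out the process. This answers much of the concern about consequences. It does not remove the conflict, because the protocol uses the same word for both tests and does not say that they are meant to differ.

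Three stronger readings are tempting and are not supported:

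- *Qualifying SAEs will be missed because the Sponsor screens from the PI's field.* No section says that it does.
- *Whether an Extension event is recorded depends on which of the two thresholds is used.* Section 9.6.3.7 is confined to expedited SAE reports and 9.6.3.5 holds the only AE causality scale, so a reader would probably apply the latter to TRAEs. The gap is that TRAE is undefined.
- *Late scar events cannot be compared between halves.* POSAS and photographs compare scar appearance by side, including thickness, relief, pain and itch. Only what they do not capture is lost.

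Nor do the documents show that most local events would be coded Not Related; that is conjecture.

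It is also fair to say that a two-level scale and related-only recording are legitimate choices for an observational phase whose sole objective is efficacy, and that the late-SAE trigger, which rests on what the PI feels, can operate without a coded field. For that reason the procedure item is optional. The case for recording incision-site AEs by side stands: the question is already asked at each visit, and the side comparison is the design's own tool.

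**Conclusion.** The point holds as an inconsistency in safety definitions with limited but real consequences. An unexpected SAE with little but some possibility of drug causation is Not Related under 9.6.3.5 and meets the expedited definition in 9.6.3.7. The likely effect is inconsistent expediting between cases or assessors, not loss of the initial report. The procedure trigger in 9.6.3.6 has no counterpart on the scale. In the Extension, incision-site AEs attributed to surgery leave no AE record by side, although scar appearance is still documented.

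This rests on two assumptions. The first is that no document outside the protocol already reconciles the wording. The second is that the all-causality 24-hour rule continues to apply in the Extension. Section 9.6.3.6 does not say how that rule fits with its relatedness trigger for SAEs more than 30 days after dosing, and the whole Extension lies beyond that point. The size cannot be quantified. Sample size, alpha and the planned efficacy analysis are unaffected. The change is worth making because it is cheap; nothing here says which threshold is the right one.

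**What to change.** 1. Reconcile 9.6.3.5, 9.6.3.6, 9.6.3.7 and the TRAE entry to one stated definition of related, saying whether it covers drug, procedure or both. State that the expedited screen applies it to every SAE, whatever the PI's code.
2. Optionally, add a yes/no eCRF item for causality of the study procedure (excision or abdominoplasty), so that the late-SAE trigger has a matching record.
3. In the Extension, record AEs located at the abdominoplasty incision by side regardless of causality. Keep related-only recording for all other events. The AE form already asks for corrective treatment, so this also captures treatment of such events.

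The cost is wording in the sections named, including the Extension recording rule in 9.6.3, one or two eCRF fields, and a few more local AE records. No extra visit or treatment change is needed.

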#### **9.6.3.8 Pregnancy**

During Parts A and B, all female subjects of childbearing potential must use an effective method of birth control (as defined in Section 5.1) during the course of the study, in a manner such that risk of contraceptive failure is minimized. Abstinence is allowed as a birth control method.

Before enrolling a female subject of childbearing potential in this clinical trial, the PI must review the following information about study participation:

- Informed consent requirements
- Contraceptives in current use

Following review of this information and appropriate subject counseling, the PI or designee (obtaining the consent) and the subject must sign the informed consent before study enrolment.

During the study, all female subjects of childbearing potential should be instructed to contact the PI immediately if they suspect they might be pregnant (e.g., missed or late menstrual period).

If a subject or PI suspects that the subject may be pregnant prior to study enrolment, the study drug must be withheld until the results of laboratory pregnancy testing are available. If pregnancy is confirmed, the subject must not receive study drug and must not be enrolled in the study.

If pregnancy is suspected while the subject is receiving study treatment, the study drug must immediately be withheld until the result of pregnancy testing is known. If pregnancy is confirmed, the study drug will be permanently discontinued, and the subject will be followed until the pregnancy comes to term.

For Part B-Extension, all female subjects of childbearing potential are not required to use a birth control method as pregnancy will not impact their study participation. However, if they suspect they might be pregnant (e.g., missed or late menstrual period), they should be instructed to contact the PI immediately.

All confirmed pregnancies must be reported via confirmed facsimile or email transmission and must be submitted on an Unanticipated Problem Reporting form within 24 hours of the PI's awareness of the pregnancy. Any pregnancy complications that meet the criteria of a SAE (e.g., a spontaneous abortion, stillbirth, congenital anomaly, etc.) are considered SAEs. The SAE form must be submitted of PI awareness using the same reporting as procedure for an SAE under Section 9.6.3.6.

## 10 STATISTICS

All statistical processing will be performed using SAS® version 9.4 or later. Statistical significance will be based on two-tailed tests of the null hypothesis resulting in p-values of 0.05 or less. A statistical analysis plan (SAP), describing all statistical analyses will be provided as a separate document. The SAP will be finalized prior to unblinding of the study treatments.

### 10.1 Sample Size Determination

Approximately 25 subjects will be enrolled. This is a POC study and a formal sample size justification is not required for this study. It is the opinion of the Sponsor that a total of 25 subjects will be sufficient to achieve the objectives of the study.

### 10.2 Assessments of Efficacy

Efficacy analyses will be conducted on an intent-to-treat (ITT) basis (see Section 10.4).

For categorical parameters, the number and percentage of subjects/observations in each category will be presented. The denominator will be based on the number of subjects/observations appropriate for the purpose of analysis. For continuous parameters, descriptive statistics will include n (number of subjects or observations), mean, standard deviation, median, and range.

Comparisons between treatment groups will be performed using parametric or non-parametric testing, as appropriate.

### 10.3 Assessment of Safety

For Parts A and B, safety analysis will be conducted on the Safety Population (SAFT), by tabulations of AEs, safety laboratory parameters and immunogenicity outcomes.

Subjects will be followed for AEs (local and systemic) throughout the study. Events specific to treatment sites will be recorded by excision site (Study Part A) and per side (Study Part B) to allow comparison of study treatments.

For Part B Extension, Safety analysis will be conducted on the ITT population. Subjects will be followed for Treatment-Related AEs (local and systemic) throughout the study.

#### 10.3.1 Adverse Events

All AEs occurring during the study will be recorded and classified on the basis of MedDRA terminology. Descriptions of AEs will include the date of onset, the date the AE ended, the severity of the AE, the relationship to study medication, the action taken regarding study medication usage, the action taken to treat the AE, and the outcome. All reported treatment-emergent AEs (TEAEs) will be summarized by the number of Subjects reporting AEs, system organ class, severity, seriousness, and relationship to study medication. TEAEs are those AEs with an onset on or after the date of initial IP exposure.

AEs will be summarized by treatment group and severity, and by treatment group and relationship to IP. Each subject will be counted only once within a system organ class or a preferred term by using the AEs with the greatest relationship within each category.

All information pertaining to AEs noted during the study will be listed by subject, detailing verbatim given by the PI, preferred term, system organ class, start date, stop date, severity, actions taken, and drug relatedness.

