Study Design	
This is a multicenter, double-blind study comparing the safety of SLI-F06 to control formulation buffer (vehicle), as well as comparing the improvement in scar appearance and wound strength. Each subject will serve as his or her own control.
 
The study is divided into 2 parts where Part A is a Phase I safety/proof of concept study of small scars pre-abdominoplasty, and Part B is a Phase IIa study of post-abdominoplasty scars. In Part A of the study (i.e., Phase I safety/proof-of-concept), subjects desiring abdominoplasty and who consent to participate in the study will have their abdominoplasty site mapped to accommodate 12, 14 or 18 excisions depending on pannus size for standardized 3 cm length excisions (see Section 6.5).
 
Subjects will be allocated to 2 groups with different durations of post-excision follow-up (i.e., 12 weeks or 8 weeks pre-abdominoplasty) according to when they were enrolled into the study. All participants will be enrolled in or transferred to the 12-week pre-abdominoplasty group (Group 1). However, if
		

	
consented participants, who are assigned to Group 2 (8-week pre-abdominoplasty), cannot transfer to Group 1, they will remain in Group 2. Each excision site will be treated post-operatively in precisely the same manner. Following completion of the follow-up period, the entire abdominoplasty site will be harvested and sent for analyses of histopathology and tensile strength.
 
In Part B of the study (i.e., Phase IIa), ALL subjects who complete Part A will be randomly assigned to receive injections of SLI-F06 along one half (left or right) of the abdominoplasty incision and control injections along the other half. Injections will be on both sides of the incision. The subject will undergo routine wound care and will attend study follow-up visits following abdominoplasty at Day 8 and at Months 1, 2, 3, 6, 9, and 12.
 
Participants will then be invited to participate in an observational extension of the study, Part B Extension. Numbering and timing of study visits will be extended from Visit 8b (M12) of Part B. The subject will attend study visits at Months 15, 18, 21 and 24 where they will undergo POSAS assessments (PI and Subject) and abdominal photography. No further treatments will be administered during this observational extension of the study.

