### 6.2 Randomization

A hardcopy computer generated “Randomization Schedules” will link a bilateral (left, right) treatment assignment to each Subject Number (Section 6.1). Randomization to treatment assignment for Part A will be independent of Part B randomization. The Randomization Schedule will be maintained by the Independent Drug Reconstitutor (Section 6.3). During Part A, all excisions to be treated with SLI-F06 for a given subject will be on one side of the mapped area (i.e., left side or right side) and vehicle treated excisions will be on the other side of the mapped area. During Part B, one side of the abdominoplasty incision will be treated with SLI-F06 (i.e., left side or right side) and the other side of the incision will be treated with vehicle.

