#### **6.5.4 Sequence of Excisions**

Bilateral matched excisions (e.g., R1/L1, R2/L2, etc.) are to be performed in sequence. Each individual excision should be injected and then closed prior to performing the next excision (i.e., do not perform all of the excisions, followed by all of the closures). Injection of study drug is to be performed before closure (i.e., excise skin, undermine if needed, hemostasis, inject study drug, then skin closure).

It is acknowledged that during the excision process, the topography of the pannus will change and the final placement, orientation, and number of excisions may not match pre-defined pannus mapping. In such cases, the abdominoplasty map should be updated and annotated accordingly in order to match the final placement, orientation, and number of excisions.

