### **10.4.2 Populations for Safety Analysis**

The SAFT population will be used for safety analysis and will consist of all randomized subjects who received one injection of IP, and will be analyzed as per the treatment actually received.

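### The by-treatment adverse event tables in Section 10.3.1, and the Synopsis safety comparison with vehicle, are not limited to treatment-site events, the only events this within-subject design can attribute to a treatment

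*Protocol*

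**What the plan says.** **Design.** The Synopsis states that "Each subject will serve as his or her own control". Section 6.2 adds that in Part A "all excisions to be treated with SLI-F06 for a given subject will be on one side of the mapped area", with vehicle on the other side. Section 6.5.4 shows that both treatments are given in one session: "Bilateral matched excisions (e.g., R1/L1, R2/L2, etc.) are to be performed in sequence". For Part B, Section 6.2 says "During Part B, one side of the abdominoplasty incision will be treated with SLI-F06 (i.e., left side or right side"), and the other half of the incision gets vehicle. Section 9.3.1 places all Part B injections at Visit 1b.

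**Safety aim.** Safety and tolerability are the primary objectives of Parts A and B (Section 2). The Synopsis describes the study as "comparing the safety of SLI-F06 to control formulation buffer (vehicle").

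**Safety analysis.** Section 10.3 follows subjects for both local and systemic AEs and then says: "Events specific to treatment sites will be recorded by excision site (Study Part A) and per side (Study Part B) to allow comparison of study" …, that is, of SLI-F06 with vehicle. Section 10.3.1 first plans a summary of all treatment-emergent AEs with no treatment split. Its next paragraph says: "AEs will be summarized by treatment group and severity, and by treatment group and relationship to IP", counting each subject once within a system organ class or preferred term.

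**The concern.** The by-treatment sentence in 10.3.1 suits a parallel-group trial, where each subject belongs to one arm. Here each fully treated subject belongs to both. A fever, a headache or a rash away from the wounds occurs in a person exposed to both products on the same day, so it has no treatment group. The protocol gives no rule for placing it.

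This is a first-in-human study with safety as its primary objective, and no data monitoring committee is planned (Section 12.5). A table that shows systemic events beside a vehicle column could be read as controlled evidence. Equal columns would look reassuring and unequal ones would look like a signal, yet neither would carry information about the drug.

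**Working it through.** The protocol gives no figure to reproduce on this point, so the check sets the sections against each other and follows the rule through.

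**1. Who is in each column?** About 25 subjects are planned (Section 10.1). All are to receive both treatments, so the same 25 or so people are the denominator of the SLI-F06 column and of the vehicle column. Moving to Part B does not help. Subjects enter it after receiving SLI-F06 in Part A (60, 70 or 90 mg by pannus size, Section 7.5), so no vehicle-only period exists after first dosing.

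**2. Which events have a treatment?** Under Section 10.3, those specific to a treatment site, because they are recorded by excision site or by side. For these the within-subject comparison is valid. Systemic events get no such label.

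**3. Apply the 10.3.1 sentence to a systemic event.** Let *n* be the number of subjects and *s* the number with a given systemic AE.
- Counted under both treatments: *s/n* against *s/n*, a difference of 0 for every *s*, whatever the drug does.
- Counted under one treatment: *s/n* against 0, or the reverse. The difference is plus or minus *s/n* and depends only on who chose the column.

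**4. Follow it into the overall any-AE row.** Let *a* and *b* be the numbers of subjects with a site-specific AE on the SLI-F06 and vehicle sides, and suppose for simplicity that none of them also has a systemic AE.
- Local events only: *a* against *b*.
- Systemic events in both columns: (*a + s*) against (*b + s*). The difference stays *a − b*, but the ratio is pulled towards 1.
- Systemic events in one column: the difference moves by *s* in that column's direction.

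If the two groups overlap, counting each subject once also shrinks the difference in the both-columns case. A subject with a local event on one side only and a systemic event is already in one column and is added to the other.

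**5. Which rows stay sound?** A preferred term that occurs only at the wound receives no systemic events and is unchanged. The exceptions are terms that can occur both at and away from the site (Section 9.6.3.1 names pain and pruritus among wound findings) and organ-class rows that mix the two kinds of event.

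**6. What can the systemic data say once reported alone?** They are single-arm data with one denominator. Taking *n* = 25:
- Zero events gives an upper 95% bound of 1 − 0.05^(1/25) = 11.3% one-sided, or 1 − 0.025^(1/25) = 13.7% two-sided exact.
- The chance of at least one event is 1 − 0.95^25 = 72% at a true rate of 5%, and 1 − 0.90^25 = 93% at 10%.

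**The case against.** Much can be said for the protocol, and most of it stands.

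- **The sentence does not say all AEs.** A reader might infer that 10.3.1 orders every AE into a treatment column. It does not: the word all belongs to the treatment-emergent summary, which has no treatment split and suits systemic events.
- **Section 10.3 already points to a local comparison.** It assigns only site-specific events to a treatment, and 10.3.1 sits beneath it. This is a fair reading, but 10.3.1 neither repeats nor cites the limit.
- **Nothing forces a systemic event into a column.** A separate category for events that are not site-specific would be compatible with the text, and a statistical analysis plan may supply one. The point is therefore not a missing table layout. It is that a stated rule, read as written, cannot validly be applied to some of the events it covers.
- **The vehicle comparison is not empty.** A reader might infer that no safety comparison is possible, or that the local one is spoiled. Neither follows: the side-level comparison is sound and local preferred-term rows largely keep their counts. The objectives speak of assessing safety rather than comparing it, and Section 4.1 words the comparison as scar appearance and wound strength. Only the Synopsis words it too widely.
- **Section 10.4.2 is not an error.** It says subjects "will be analyzed as per the treatment actually received". One might object that everyone receives both, but the wording has a sensible meaning at side level, for example if syringes were swapped.
- **No size can be given for this trial.** The protocol contains no event counts, so any numerical ratio would rest on invented ones.

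**Conclusion.** The point holds in limited form. Section 10.3.1 states a by-treatment AE summary without confining it to site- or side-specific events, and the Synopsis states a safety comparison with vehicle without confining it to local safety. For systemic AEs the first yields either a difference of exactly 0 by construction or an arbitrary one, and the second claims more than the design can give. The effect lies mainly in the overall any-AE row and the systemic rows.

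This rests on two facts in the protocol: both treatments are given at the same visit, and no rule places systemic events. It also assumes that the by-treatment sentence is applied as written. If the statistical analysis plan already restricts those tables, the practical harm is avoided and only the protocol wording needs correcting. No sample size, power or error-rate figure is affected.

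**What to change.** 1. **Section 10.3.1:** limit the summaries by treatment group (by severity and by relationship) to AEs specific to a treatment site or side, tabulated by the treatment received there. State that systemic AEs are reported once, for all subjects exposed to SLI-F06, in the unsplit treatment-emergent summary already planned, with no vehicle column.
2. **Synopsis, Study Design:** limit the safety comparison with vehicle to local (treatment-site) safety, and state that systemic safety is uncontrolled.

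The cost is protocol wording and table layout. Data collection need not change, because Section 10.3 already has local events recorded by site or side. The small downside is a narrower stated safety comparison.
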